bowel disease, irritable bowel syndrome, chronic constipation, severe constipation (in the opinion of the Investigator), history of frequent diarrhea, history of surgery for weight loss, gastroparesis, systemic disease that might affect gut motility according to the Investigator, medication managed reflux and/or clinically important lactose intolerance].

- Participant has a condition the Investigator believes would interfere with his ability to provide informed consent, comply with the study protocol, which might confound the interpretation of the study results, or put the participant at undue risk.

Sample Size. Our primary outcome goal is to demonstrate significant differences between serving sizes of exogenous ketone compounds in plasma total ketone AUC. Previous work using the BHB Monoester compared to ketone salt products demonstrated that a sample size of 12 participants was required to detect a difference in BHB AUC of ~20% (80 mM.h⁻¹) between ketone compounds with alpha set at 0.5 and power at 0.8. This sample size will also give sufficient power to address our secondary aims which include differences in peak ketone concentrations, plasma BHB, AcAc, breath acetone, glucose, insulin, free-fatty acids, amino acids, blood chemistry, pH, gas exchange values and heart rate. Based upon prior studies, we expect up to 20% of participants will withdraw from the study after recruitment, and therefore we will plan to recruit 15 participants.

Recruitment:

Recruitment will occur through well-established methods at OSU, which include word of mouth, ResearchMatch database, social media engagement and flyers. For this study we will specifically aim to recruit cadets in the OSU Reserve Officers Training Corps (ROTC), who have participated in research on ketosis in the past and been supported by their cadre to enroll in our research projects (see letters of support from Army, Navy, and Air Force ROTC leadership).

Randomization:

If a participant meets all inclusion and none of the exclusion criteria, the following will occur at the end of the screening visit:

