Participants will then consume the Study Product that they were randomly allocated for that Test Day (details of Study Products below). Time of ingestion should be +/- 60 minutes from the time established at Test Day 1; they will be given 5 minutes to consume the Product. After Study Product consumption, they will remain at the study center for ~4h, with blood and breath sampling occurring at regular intervals (see Figure 2). A total of 7 whole blood samples (7x ~8 mL each= ~56mL) will be collected each Test Day. Capillary blood samples and breath acetone readings will be collected at the same time as whole blood samples. The fitted face mask will be worn for 10 minutes each hour to collect respiratory gas measures. Participants will be asked to collect all urine passed during the test in a provided container, and asked to fully void their bladder and collect the urine at the end of the test day. Participants will complete satiety questionnaires each hour, and will complete a BTQ at the end of the Test Day.

Participants will be asked to minimize ambulatory movement during the Test Day. Non caloric beverages (i.e.,water) will be permitted *ad libitum* and intake volumes will be recorded. At the end of each Test Day, the heart rate monitor and IV cannula will be

removed and a dressing will be applied to the cannula site. Participants will be given a snack to consume.

Sample Processing and Analysis

Blood Processing: Whole blood collected through the IV cannula will be either 1) immediately stabilized for AcAc analysis using a validated method, 2) processed to plasma (EDTA tubes), or 3) serum (clot activator serum collection tubes) and then snap frozen in liquid nitrogen for storage prior to analysis (details below). We will collect capillary blood samples for real-time analysis of blood BHB and glucose concentration, using commercially available test strips and a handheld monitor (KetoMojo, CA, USA), this will also allow comparison of ketone values obtained via different methods.

Blood Sample Analytical Methods:

- *Ketones* will be determined by multiple methods to provide a robust measure of ketosis and allow cross validation. Firstly: by capillary BHB concentrations obtained from a finger stick using a handheld device (KetoMojo, USA). Secondly: plasma ketones (AcAc, R-BHB and S-BHB) will be measured using ultra-performance liquid chromatography – tandem mass spectrometry (LC-MS). Thirdly: Continuous Ketone Monitoring (see details below)

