Respiratory Gases: Respiratory gas exchange will be assessed using breath-by-breath gas exchange measurements of VO₂ and VCO₂ recorded every 30-sec. Participants will wear a fitted face mask connected to a metabolic cart for 10 minutes every hour (TrueOne 2400, ParvoMedics, UT, USA). Participants will also complete one exhale into a high-resolution portable breath acetone meter (Readout Health, USA) for determination of breath acetone.

Heart rate and heart rate variability: At the start of each Test Day participants will don a Bluetooth chest strap that is sensitive enough to detect R-R intervals (Polar Electro, Finland). The chest strap will be worn for the duration of each Test Day and removed before the participant leaves the study center.

Beverage Tolerability Questionnaire: The BTQ used in this study is similar to that used in previous tolerability studies^{27,28,29,30}. Ten tolerability issues are included in the BTQ: gas/flatulence, nausea, vomiting, abdominal cramping, stomach rumbling, burping, reflux (heartburn), diarrhea, headache, and dizziness. Participants are asked if the issue was present (pre- beverage - baseline) or had occurred since they took the study beverage (post-beverage – 4h) at the following intensities: none, mild (awareness of symptoms but easily tolerated), moderate (discomfort enough to interfere with but not prevent daily activity) or severe (unable to perform usual activity). These correspond to scores of 0–3, respectively for each issue, giving a maximal composite score, defined as the sum of the ten items, of 30.

Satiety Visual Analogue Scale: We will use a 3-item visual analogue scale, that assesses hunger, fullness and desire to eat by participant's marking on a line anchored at either end with 'not at all' and 'extremely.' Distance along the line is measured in mm.

STUDY PRODUCTS

Background: The four exogenous ketone compounds (BHB Monoester, C6 Diester, AcAc Diester, (R) 1,3 Butanediol) will be used all have GRAS status as a dietary ingredient (**Table 1**). BHB Monoester, C6 Diester, and (R) 1,3 Butanediol are commercially available in the products 'deltaG' (TdeltaS Global, FL, USA), 'Metabolic Switch' (Juvenescence Ltd,

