C6 Di-ester	180 mg/kg and 360 mg/kg	Ready to drink beverage	Water, whey protein concentrate, modified gum acacia, natural and artificial flavors, cocoa powder, lecithin, fruit and vegetable juice for color, bisulfate of soda, caramel color, acesulfame K, cellulose gum, pectin (standardized with sucrose), sucralose, xanthan gum, canola oil [DAIRY AND SOY]	Metabolic Switch (Juvenescence Ltd, NJ, USA)
AcAc Di-ester	180 mg/kg and 360 mg/kg	1.5g capsules	Geltain (bovine), glycerin, water.	KetoLogic Ketone Di-ester Softgels (Disruptive Nutrition LLC)
(R)-1,3 butanediol	180 mg/kg and 360 mg/kg	Undiluted liquid ingredient – mixed on site with water and sweetener	None	Ketone-IQ (H.V.M.N. Inc, FL, USA)
Control	NA	Beverage	Water, canola oil, whey protein concentrate, modified gum acacia, natural and artificial flavors, cocoa powder, lecithin, fruit and vegetable juice for color, bisulfate of soda, caramel color, acesulfame K, cellulose gum, pectin (standardized with sucrose), sucralose, xanthan gum, canola oil [DAIRY AND SOY]	National Food Laboratory, NY, USA

DATA ANALYSIS AND STATISTICAL METHODS

Primary outcomes

- Difference in total plasma ketone appearance (AUC) between the two serving sizes of study products and control

Secondary outcomes

- Differences in other blood ketone kinetic parameters (peak concentration, time of peak concentration, AUC of different ketone bodies, capillary ketone concentrations).
- Differences in urine and breath ketone excretion
- Differences in blood metabolites (glucose, free fatty acids, alanine).
- Differences in heart rate and heart rate variability and blood pressure
- Differences in subjective tolerability and subjective satiety measured by questionnaires
- Differences in blood hormones (insulin, ghrelin).
- Differences in blood acid-base balance (bicarbonate, strong ions)
- Differences in respiratory gas exchange (VO₂ and VCO₂)

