Statistical Plan. Statistical analysis of data will take place on completion of the study in collaboration with Buck Bioinformatics Core. Participant data will be included if they have completed at least 2 serving sizes of one exogenous ketone product AND the control Test Days (i.e., BHB- mono-ester 180 mg/kg, BHB mono-ester 360 mg/kg and Control). Any incomplete exogenous ketone compounds (i.e., participant completed C6 Di-ester 180 m/kg and AcAc ester at 360 mg/kg) will be excluded from the analysis. All decisions regarding exclusion from the analysis population will be documented prior to database lock. Missing data will not be imputed, and only observed data will be included in the statistical analysis.

Repeated measure group x time ANOVA (or a non-parametric alternative) will be performed following initial tests to ensure sphericity is not violated. We will compare data between control group vs. each individual exogenous ketone at both doses (i.e., control vs BHB-mono ester (180 mg/kg) vs BHB-mono-ester (360 mg/kg). We will also test for condition x time interactions. If significance is detected, post-hoc comparisons will be made using Tukey's HSD tests (or non-parametric alternative) to correct for multiple comparisons. Significance will be accepted at an alpha level of P < 0.05.

Other data processing:

- Area Under the Curve (AUC) will be calculated using the Trapezoid Rule.
- Maximal/minimal concentration data (C_{max} and C_{min}) and time of maximal/minimal concentration (T_{max} and T_{min}) will be extracted from the raw data.

- A composite tolerability score is calculated by adding the scores (0 -3, corresponding to none, mild, moderate, severe) of all ten listed symptoms.

STUDY MONITORING

Concomitant Medication/Supplements and Treatment

All concomitant medications/supplements used 1 months prior to Screening Visit and during the study will be reported to the study personnel for assessment and recorded in the participant's study documents.

Adverse Event Monitoring

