An AE is defined as any untoward medical occurrence in an investigation participant following written informed consent that does not necessarily have a causal relationship with the study product. An AE can be any unfavorable or unintended sign (including an abnormal finding), symptom, or disease temporally associated with the use of an investigational product, whether or not related to the investigational product. This includes any occurrence that is new in onset or aggravated in severity or frequency from the baseline condition, or abnormal results of diagnostic procedures (including laboratory test abnormalities).

Some side effects or GI symptoms could occur as an outcome of these dietary interventions; side effects listed in the beverage tolerability questions and reported will not be categorized as AEs but recorded as study outcomes. Side effects, outside of what is expected as a result of study product consumption, reported by participants and judged by the Investigators as medically relevant events and related to study product will be recorded as AEs.

Events should be considered AEs if they:

- Result in discontinuation from the study,
- Require treatment or any other therapeutic intervention,
- Require further diagnostic evaluation (excluding a repetition of the same procedure to confirm the abnormality),
- Are associated with clinical signs or symptoms judged by the Investigator to have a significant clinical impact.

Grading and Severity

The Investigator will evaluate all AEs with respect to their severity, and record the outcome and action taken on the AE study documents . AEs will be graded as:

Mild: Awareness of symptoms but easily tolerated

Moderate: Discomfort enough to interfere with but not prevent daily activity

Severe: Unable to perform usual activity

Relationship

The Investigator will also judge the likelihood that the AE was related to the study beverage and document this on the appropriate study documents as:

NOT RELATED	This category applies to those adverse experiences which, after careful consideration, are clearly and incontrovertibly due to extraneous causes (disease, environment, etc.).
UNLIKELY	In general, this category can be considered applicable to those experiences that after careful medical consideration at the time they are evaluated, are judged to be, unlikely related to the study beverage.

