- A participant requests discontinuation;
- The Investigator initiates removal for medical or compliance reasons;
- Occurrence of any AE or condition that could, in the Investigator's opinion, interfere with the evaluation of the effect of the study beverage or put the participant at undue risk.

It is understood by all concerned that an excessive rate of withdrawals can render the study uninterpretable, therefore, unnecessary withdrawal of participants should be avoided. Should a participant decide to withdraw, all efforts will be made to complete and report observations as thoroughly as possible. In the event that a participant is withdrawn from the study, the reason for the withdrawal will be documented in the eCRF.

References

5. Myette-Côté É, Caldwell HG, Ainslie PN, Clarke K, Little JP. A ketone monoester drink reduces the glycemic response to an oral glucose challenge in individuals with obesity: a randomized trial. *The American Journal of Clinical Nutrition*. 2019;110(6):1491-1501.

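### The complete-set rule has no exception for tolerability, so a recorded score can be dropped because its symptoms led to withdrawal

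*Protocol*

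**What the plan says.** The Statistical Plan in the Protocol sets one rule for entering the analysis: "Participant data will be included if they have completed at least 2 serving sizes of one exogenous ketone product AND the control Test Days". It continues with "Any incomplete exogenous ketone compounds", which are left out. The rule names no outcome and exempts none. The same section rules out imputation and limits the analysis to observed data, but this does not bring back observed data that the rule has already removed.

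Tolerability falls under this plan. The secondary outcomes include "Differences in subjective tolerability and subjective satiety measured by questionnaires". The Beverage Tolerability Questionnaire section describes ten symptoms scored 0 to 3, "giving a maximal composite score, defined as the sum of the ten items, of 30", and the Statistical Plan repeats that composite. Under Testing Days, participants "will complete a BTQ at the end of the Test Day", so the score normally exists before any later withdrawal.

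Two other sections bear on participants who stop. Adverse Event Monitoring treats questionnaire symptoms as study outcomes and not as adverse events, but lists among the events to be considered adverse events those that "Result in discontinuation from the study". Withdrawal of Participants from the Study says that "all efforts will be made to complete and report observations as thoroughly as possible" and requires the reason to be documented.

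**The concern.** For most outcomes, a rule that demands both servings and control costs some data but has no direct link to the value being measured. Tolerability is different. Bad symptoms after a serving are a plausible reason to leave, and leaving makes that product's set incomplete unless the other two days are already done. The score that recorded the symptoms is then excluded because of what it recorded.

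The scores at risk are those of the participants who tolerated a serving worst, so the error runs one way: a poorly tolerated product or serving looks better than it is. The Protocol aims to help choose among ketone products, and tolerability by product and serving bears on that choice.

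**Working it through.** **Inputs from the Protocol.** Nine conditions in random order (Randomization): four products at two servings, plus control. 15 recruited for 12 evaluable. On attrition, Sample Size says "we expect up to 20% of participants will withdraw from the study after recruitment". Check: 12/(1 - 0.20) = 15, as stated, so the planned withdrawals are up to 3 of 15, from any cause.

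**Assumptions, not in the Protocol.** The day that triggers withdrawal counts as completed and has a questionnaire. Withdrawal day k is equally likely over days 1 to 8 (after day 9 nothing is left to withdraw from). Participants who stop score d points above the others at that serving. All others are treated as having complete sets.

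**Chance that the triggering score is kept.** Given an active serving on day k, the other eight conditions fall at random on the other eight days. The other serving and control must both lie among the k-1 earlier days:

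P(kept) = (k-1)(k-2)/(8 × 7) = (k-1)(k-2)/56

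| Day k | 1 | 2 | 3 | 4 | 5 | 6 | 7 | 8 |
|---|---|---|---|---|---|---|---|---|
| Kept | 0% | 0% | 3.6% | 10.7% | 21.4% | 35.7% | 53.6% | 75.0% |

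The numerators sum to 0 + 0 + 2 + 6 + 12 + 20 + 30 + 42 = 112. The mean is 112/(56 × 8) = 0.25, so on average 75% of such scores are dropped. A simulation of random orders agreed.

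**Effect on the mean score at a serving.** With m of 15 stopping at that serving, of whom K remain in the analysed set, K ~ Bin(m, 0.25):

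understatement = d × {m/15 - E[K/(15 - m + K)]}

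- m = 1: E = 0.25 × 1/15 = 0.0167. Understatement = (0.0667 - 0.0167)d = 0.05d, which is 0.25 points at d = 5.
- m = 2: E = 0.375 × 1/14 + 0.0625 × 2/15 = 0.0351. Understatement = (0.1333 - 0.0351)d = 0.098d.
- m = 3: E = 0.4219 × 1/13 + 0.1406 × 2/14 + 0.0156 × 3/15 = 0.0557. Understatement = (0.2000 - 0.0557)d = 0.144d, which is 0.72 points at d = 5.

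**Three symptom withdrawals spread evenly over the eight active servings.** The number at any one serving is Bin(3, 1/8), with probabilities 0.2871, 0.0410 and 0.0020 for 1, 2 and 3:

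0.2871 × 0.05d + 0.0410 × 0.098d + 0.0020 × 0.144d = 0.019d

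That is about 0.09 points per serving at d = 5 and 0.19 at d = 10.

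**The case against.** The strongest reply is that the rule serves the design. The planned comparison is control against both servings of one product within person, by repeated-measures ANOVA, which needs complete triplets. Exclusion could be read as exclusion from that comparison only, leaving descriptive reporting open, and a SAP that is not shown might add a tolerability summary. Part of this stands: the rule suits the AUC analysis. But the Protocol itself fixes one general rule, lists tolerability among the outcomes it governs, and nowhere returns an excluded score to the comparison.

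The size is also fairly contested. The 20% is an any-cause ceiling, no share for symptoms is given, and no value of d is given. With withdrawals spread over eight servings the bias is small on a 0 to 30 scale.

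Four stronger readings are tempting, and the document does not support them.

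- A reader might infer that intolerance goes unrecorded. It does not: an event leading to discontinuation is to be considered an adverse event, and the reason for withdrawal is documented.
- A reader might infer that a true 20% share stopping for symptoms would be reported as 5.6%, the m = 3 figure above. The plan does not estimate that share from the analysed set, and withdrawals can be counted from the separate records.
- A reader might add participants who decline one serving and carry on. The Statistical Plan foresees incomplete products, but the withdrawal section describes only removal from the study, so that route is inferred.
- A reader might fear for the primary AUC comparison. With 3 of 15 withdrawing evenly after days 1 to 8, a set is complete with probability k(k-1)(k-2)/504, on average 0.1875, leaving 12 + 3 × 0.1875 = 12.56 per product, above the planned 12.

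**Conclusion.** The point holds in a limited form. As written, the rule can drop an observed tolerability score because of the symptoms it records, and the resulting bias is towards better tolerability. What is lost is the score in the comparison, not the record of the withdrawal.

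The direction is clear if symptoms cause withdrawal. The amount cannot be known from the document. About 0.02d per serving (three symptom withdrawals spread evenly) to 0.05d (one at a given serving) is a moderate range. The figure of 0.14d, with all planned withdrawals due to symptoms at one serving, is an upper case and should not be read as the expected result. These figures rest on random order, an even spread of withdrawal over days 1 to 8, and an assumed d. The correction is worth making because it is nearly free. The primary outcome is not at issue.

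**What to change.** In the Statistical Plan:

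1. Limit the complete-set rule to the outcomes other than tolerability.
2. Summarise the tolerability score by product and serving for every serving taken with a recorded questionnaire, whether or not the other serving or control was completed.
3. If tolerability is compared formally, use a method that accepts incomplete sets, such as a mixed model with participant as a random effect, and state that it relies on missing-at-random. The planned repeated-measures ANOVA would drop the incomplete sets again.
4. Tabulate, by product and serving, the test days or participation stopped for symptoms. This is still needed because a participant who leaves before the end-of-day questionnaire has no score.

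The cost is a few sentences and one table from data already collected. The downside is that the tolerability set will differ in size by product and from the set for the other outcomes, and raw means from unequal sets mix between-person differences into a within-person comparison. The number of participants behind each mean should therefore be shown.

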*Strategies to Augment Ketosis:
Optimization of Ketone
Delivery(STAK:OK'd)*

The Ohio State University

IRB Approval July 26, 2022

IRB# 2022H0160

Strategies to Augment Ketosis: Optimization of Ketone Delivery (STAK: OK'd) IRB Protocol

Title: Optimization of Ketone Delivery

Short title: STAK-OK'd

PI: [name], RD
Professor, Department of Human Sciences
The Ohio State University
[name]
[name]
Office: [contact] | [contact]

Co-PI: [name], DPhil
Lead Translational Scientist
The Buck Institute for Research on Aging
[name]
[name]
Office: [contact] | [contact]

ABBREVIATIONS

AcAc	Acetoacetate
BHB	Beta hydroxybutyrate
KE	Ketone ester
BDO	(R)-1,3 Butanediol
BTQ	Beverage tolerability questionnaire
LBM	Lean body mass
LC-MS	Liquid chromatography – mass spectrometry
VO ₂	Oxygen uptake
VCO ₂	Carbon dioxide release
GRAS	Generally recognized as safe
AUC	Area under the curve
C _{max}	Maximal concentration
C _{min}	Minimal concentration
T _{max}	Time of maximal concentration
T _{min}	Time of minimal concentration
mL	milliliters
mg	Milligrams
h	Hour
ANOVA	Analysis of variance
AE	Adverse event
USG	Urine Specific Gravity

STUDY SYNOPSIS

Study Title	Optimization of Ketone Delivery
Short Title	STAK-OK'd
Study Design	Open label, randomized, placebo controlled, 9-arm cross over
Study Participants	
 • Healthy men, aged 20 -30 years old, BMI between 18 and 29 kg/m²
Planned Sample Size	An evaluable sample of 12 participants/group is required; to allow for 20% attrition a final sample size of 15 is planned.
Study Products	
 1. BHB Mono-ester 2. C6 Ketone Di-ester 3. AcAc Di-ester 4. (R)-1,3 butanediol 5. Control 
All study products are generally recognized as safe (GRAS) food ingredients.

Serving Sizes	
 1. 180 mg/kg of lean body mass 2. 360 mg/kg of lean body mass
Planned Study Period	September 2022 – September 2023
OUTCOMES	
Primary	Difference in total plasma ketone appearance (AUC) between the two serving sizes of study products and control.

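### Repeated-measures ANOVA with no imputation drops a participant from a product's time-course analysis of an analyte when a single sample is lost; a mixed model would keep them

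*Protocol*

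**What the plan says.** The Statistical Plan (Protocol, Data Analysis and Statistical Methods) sets the method: "Repeated measure group x time ANOVA (or a non-parametric alternative) will be performed following initial tests to ensure sphericity is not violated". The comparison is made product by product: "We will compare data between control group vs. each individual exogenous ketone at both doses". The rule for gaps is "Missing data will not be imputed, and only observed data will be included in the statistical analysis".

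The only inclusion rule works at the level of whole Test Days: "Participant data will be included if they have completed at least 2 serving sizes of one exogenous ketone product AND the control Test Days". The section has no rule for a single sample lost within a completed day, and it names no model that accepts an incomplete profile.

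On sampling, Methods, Testing Days says "A total of 7 whole blood samples (7x ~8 mL each= ~56mL) will be collected each Test Day". Capillary and breath readings are taken at the same times. Gas exchange is measured hourly.

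On numbers, the Study Synopsis says "An evaluable sample of 12 participants/group is required; to allow for 20% attrition a final sample size of 15 is planned". The Sample Size paragraph bases this on whole participants leaving: "we expect up to 20% of participants will withdraw from the study after recruitment". It also states that the same 12 will be enough for the secondary aims, among them glucose, insulin, free fatty acids and pH.

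**The concern.** A participant can meet the plan's own inclusion rule (control and both serving sizes completed) and still be unusable in the named analysis because one of 21 values is absent. The other 20 values, all observed, are then set aside. Nothing in the protocol asks for that deletion. It follows from choosing a complete-profile method and barring imputation.

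Venous samples are drawn through a cannula kept open by saline flushes for about 4 hours on each of nine days, so it is unsafe to plan for no losses at all. The control day enters all four product analyses, so a sample lost on that day removes the participant from all four for that analyte. The set of participants analysed can then differ between analytes and between products, and each affected analysis has fewer people than the 12 on which the protocol relies for its secondary aims.

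**Working it through.** **Inputs from the protocol.** 12 evaluable and 15 recruited (Synopsis; Sample Size); 3 conditions per product analysis (Statistical Plan); 7 whole blood samples per Test Day (Testing Days). The rate of sample loss is not given, so it is an assumption and is shown as a range.

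**The plan's own figure.** 12 / (1 - 0.20) = 15, which reproduces the recruitment target. The whole 20% is used up by withdrawal: 15 x 0.80 = 12. Nothing is left for lost samples.

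**Cells.** 3 conditions x 7 samples = 21 per participant, per analyte, per product.

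**Independent loss at rate p per sample.** Expected complete participants = N x (1 - p)^21.

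| Loss per sample | (1 - p)^21 | Complete of 12 | Complete of 15 (no withdrawals) |
|---|---|---|---|
| 0.25% | 0.949 | 11.39 | 14.23 |
| 0.5% | 0.900 | 10.80 | 13.50 |
| 1% | 0.810 | 9.72 | 12.15 |
| 2% | 0.654 | 7.85 | 9.81 |
| 3% | 0.527 | 6.33 | 7.91 |

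Turned round, being left with 10 of 12 needs p = 1 - (10/12)^(1/21) = 0.86%, and being left with 6 of 12 needs p = 1 - (6/12)^(1/21) = 3.2%.

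**Chance that nobody is lost.** 12 x 21 = 252 values must all be present. At 0.5% loss, 0.995^252 = 0.28. At 1%, 0.99^252 = 0.08.

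**Shared control day.** At 1% loss, the chance that a participant misses at least one of the 7 control samples is 1 - 0.99^7 = 0.068. That is 12 x 0.068 = 0.8 participants expected to drop out of all four product analyses for that analyte.

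**Loss clustered by day.** If a fraction f of Test Days is affected, for instance by cannula failure, expected complete participants = 12 x (1 - f)^3. At f = 5%: 12 x 0.857 = 10.3. At f = 10%: 12 x 0.729 = 8.7.

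**Hourly outcomes.** If gas exchange is read at baseline and at four hourly points (an assumption), there are 3 x 5 = 15 cells. At 1% loss, 12 x 0.99^15 = 10.3 remain.

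**What each method accepts.** Data were simulated for 12 participants x 3 conditions x 7 times = 252 values, and one value was removed. A standard repeated-measures ANOVA routine refused the data as unbalanced. A linear mixed model with a random participant effect used the remaining 251 values from all 12 participants. This shows which data each method can use. It says nothing about power.

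**The case against.** **No loss rate is given, so no headcount follows from the plan.** This stands. A reader might infer that the trial is cut to roughly 6 to 10 people. That range needs independent loss of about 0.9% to 3.2% per sample. At 0.25% to 0.5% the cost is about one participant or less, and if all 15 recruits stayed, about 12 would still be complete at 1% loss.

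**Cannula failure clusters losses.** This also stands. If 5% of days fail and about half of each such day's samples are lost, overall loss is about 2.5%. Treated as independent, that would leave 12 x 0.975^21, or about 7; clustered by day, 10.3 remain.

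**The trial as a whole is not reduced.** Agreed. Deletion is per product and per analyte. The primary AUC is one summary value per Test Day and is not deleted by this route. Capillary and breath readings share the 7 time points but do not depend on the cannula, and hourly outcomes have fewer cells.

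**A loss of power cannot be quantified.** Agreed. A reader might want to turn the counts into power. The Sample Size paragraph powers BHB AUC, gives no SD and does no calculation for the time-course tests, so any such figure would rest on invented variances.

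**The plan does not contradict itself.** Strictly, a complete-participant ANOVA analyses only observed values, so the no-imputation sentence is not breached. Handling of a gap within a day is also commonly left to a SAP, which may exist. What remains is that the protocol itself names the method. The sphericity test placed before it points to the classical form, which needs complete profiles. The alternative is named only as non-parametric, and a complete-block rank test such as Friedman's has the same limit. A SAP could remove the problem only by changing the named method.

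**Conclusion.** The concern holds in a limited form. For secondary time-course outcomes, chiefly those from venous samples, the named method discards a participant's whole profile for an analyte and product when one of 21 values is missing. The withdrawal allowance does not cover that loss. The size depends on an unstated loss rate: from under one participant of 12 at 0.25% independent loss to between five and six at 3%, and less if losses cluster within days. The counts assume that 12 participants have completed the required Test Days and, for the table, that losses are independent across samples.

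The documents do not support reading this as a defect of the primary AUC analysis, as a fixed shrinkage of the trial, or as a stated drop in power. It is a poor choice of method for which a better one is readily available, and it should be changed before database lock so that the choice is not made after seeing which samples failed.

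**What to change.** For time-course outcomes, replace the repeated-measures ANOVA with a linear mixed model fitted by REML to all observed samples, with Kenward-Roger degrees of freedom. Specify:

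- fixed effects: condition, time and condition x time;
- random effects: participant and participant-by-condition;
- a within-day covariance structure that allows serial correlation, for example first-order autoregressive or spatial power, with a stated fallback if the model does not converge. Random effects alone would impose equal correlation between all samples within a day, which is doubtful for serial samples over about 4 hours.

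Keep the same contrasts per product and the no-imputation rule. The model uses partial profiles without filling in values, on the assumption that samples are missing at random.

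The cost is about one paragraph in the protocol or SAP and standard software, with no change to visits, samples or recruitment. The small downside is that the covariance structure and its fallback must be fixed in advance.
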